Further accrual of the expansion cohort was due for dose level 1, where 1 of 6 patients had experienced DLT (GVHD) within the DLT observation period. Recently, however, 1 additional patient has experienced delayed SAE with histology suggesting a possible role for remote Ipilimumab effect. Additionally, 1 other patient had a late SAE, albeit outside of the DLT window, that was concerning for treatment toxicity. We therefore further amend the protocol to enroll 2 more patients at dose level 0 to a total of 5 evaluable patients. If 1 or none of these 2 additional patients experiences DLT, dose level 0 will be declared to be the presumptive MTD and thereafter proceed to a phase 1b expansion cohort. If, however, we observe 2 DLTs at dose level 0, dose de-escalation will take place to dose level -1 and apply the decision rule above.

Amendment June 25, 2021

No DLTs were experienced during the DLT period in the final 2 patients enrolled at dose level 0. Therefore, the phase 1b expansion cohort will proceed at dose level 0.

13.5 Sample Size/Accrual Rate

The sample size will approximately range from 4-25 evaluable patients, depending on the number of dose levels tested. Based on the current practice, we anticipate that the accrual rate will be approximately 8-10 patients per year, thus requiring up to 38 months for the completion of the accrual. This projection does not count a mandatory waiting period prior to dose de-escalation. Follow-up after termination of accrual will be 1 year after the last patient ends therapy.

CONFIDENTIAL

This document is confidential. Do not disclose or use except as authorized.

13.6 Stratification Factors

None

13.7 Analysis plan

Due to limited sample size, the analysis will be primarily descriptive. AEs/SAEs will be summarized by patient, type and grade as defined by the CTCAE v4.0. Rates will be described as proportions with exact binomial confidence intervals. CR/CRI rate at day 43 also will be described as a proportion with exact binomial confidence interval. Kaplan-Meier models will be used to estimate PFS and OS at day 100 and 1 year with exact pointwise confidence intervals. Acute and chronic GVHD will be described as cumulative incidence in the competing risks framework treating death without GVHD as a competing event. The association between clinical outcomes (response, PFS and OS and acute or chronic GVHD) and correlative endpoints (e.g., circulating Teff and Treg cells, number of AML/MDS/MPN blasts and other characteristics of the BM microenvironment pre-therapy and at post-treatment relapse) will be explored using univariable Cox, Fine and Gray regression analysis or exact Wilcoxon-Rank-Sum test, as appropriate. Analyses will be carried out in SAS 9.4 or R 3.3.2 or higher.

CONFIDENTIAL

This document is confidential. Do not disclose or use except as authorized.

APPENDIX A PERFORMANCE STATUS CRITERIA

ECOG Performance Status Scale		Karnofsky Performance Scale	
Grade	Descriptions	Percent	Description
0	Normal activity. Fully active, able to carry on all pre-disease performance without restriction.	100	Normal, no complaints, no evidence of disease.
		90	Able to carry on normal activity; minor signs or symptoms of disease.
1	Symptoms, but ambulatory. Restricted in physically strenuous activity, but ambulatory and able to carry out work of a light or sedentary nature (e.g., light housework, office work).	80	Normal activity with effort; some signs or symptoms of disease.
		70	Cares for self, unable to carry on normal activity or to do active work.
2	In bed <50% of the time. Ambulatory and capable of all self-care, but unable to carry out any work activities. Up and about more than 50% of waking hours.	60	Requires occasional assistance, but is able to care for most of his/her needs.
		50	Requires considerable assistance and frequent medical care.
3	In bed >50% of the time. Capable of only limited self-care, confined to bed or chair more than 50% of waking hours.	40	Disabled, requires special care and assistance.
		30	Severely disabled, hospitalization indicated. Death not imminent.
4	100% bedridden. Completely disabled. Cannot carry on any self-care. Totally confined to bed or chair.	20	Very sick, hospitalization indicated. Death not imminent.
		10	Moribund, fatal processes progressing rapidly.
5	Dead.	0	Dead.

CONFIDENTIAL

This document is confidential. Do not disclose or use except as authorized.

Appendix B: BODY SURFACE AREA AND CREATININE CLEARANCE

Body surface area (BSA) should be calculated using Dubois formula that yields the following results in meters squared (m²):

$$\text{BSA} = (W^{0.425} \times H^{0.725}) \times 0.007184$$

where the weight is in kilograms and the height is in centimeters.

Creatinine clearance (CrCl) can be calculated using the Cockcroft-Gault equation as follows:

$$\text{CrCl (ml/min)} = \frac{(140 - \text{age}) (\text{actual wt in kg})}{72 \times \text{serum creatinine (mg/dl)}}$$

For females, use 85% of calculated CrCl value.

Note: In markedly obese participants, the Cockcroft-Gault formula will tend to overestimate the creatinine clearance. (Adipose tissue tends to contribute little creatinine requiring renal clearance.)

CONFIDENTIAL

This document is confidential. Do not disclose or use except as authorized.

Appendix C: ACUTE GVHD GRADING

Stage	Skin (Active Erythema Only)	Liver (Bilirubin)	Upper GI	Lower GI (stool output/da)
0	No active (erythematous) GVHD rash	<2 mg/dL	No or intermittent nausea, vomiting, or anorexia	Adult: <500 mL/day or <3 episodes/day
1	Maculopapular rash <25% BSA	2-3 mg/dL	Persistent nausea, vomiting or anorexia	Adult: 500-999 mL/day or episodes/day
2	Maculopapular rash 25-50% BSA	3.1-6 mg/dL		Adult: 1000-1500 mL/day episodes/day
3	Maculopapular rash >50% BSA	6.1-15 mg/dL		Adult: >1500 mL/day or > episodes/day
4	Generalized erythroderma (>50% BSA) plus bullous formation and desquamation >5% BSA	>15 mg/dL		Severe abdominal pain w/o ileus or grossly bl stool (regardless of stool volume).

Overall clinical grade (based on most severe target organ involvement):

- Grade 0: No stage 1-4 of any organ.
- Grade I: Stage 1-2 skin without liver, upper GI, or lower GI involvement.
- Grade II: Stage 3 rash and/or stage 1 liver and/or stage 1 upper GI and/or stage 1 lower GI.
- Grade III: Stage 2-3 liver and/or stage 2-3 lower GI, with stage 0-3 skin and/or stage 0-1 upper GI.
- Grade IV: Stage 4 skin, liver, or lower GI involvement, with stage 0-1 upper GI.

Adapted from Harris AC, et al. BBMT 2016; 22:4

CONFIDENTIAL

This document is confidential. Do not disclose or use except as authorized.

Appendix D: NCI COMMON TOXICITY CRITERIA

Please refer to the NIH website:

https://ctep.cancer.gov/protocoldevelopment/electronic_applications/ctc.htm#ctc_40

Forms available upon request

CONFIDENTIAL

This document is confidential. Do not disclose or use except as authorized.

Appendix E: AML RESPONSE CRITERIA

(Cheson, *et al.*, 2003)

E.1. Antitumor Effect: AML

E.1.1 Morphological Complete Remission (CR):

-Normalization of the peripheral blood absolute neutrophil count $> 1.0 \times 10^9/L$, platelets $>$ than $100 \times 10^9/L$ no residual evidence of extramedullary disease and bone marrow aspirate with $\leq 5\%$ blasts, no blasts with Auer rods.

E.1.2 Morphological Complete Remission with incomplete blood count recovery (CRi):

-Same as CR but without normalization of the peripheral blood absolute neutrophil and platelet Count

E.1.3 Relapse from CR or CRi:

-Reappearance of leukemic blasts in the peripheral blood; or $> 5\%$ blasts in the bone marrow not attributable to another cause (e.g. recovery of normal cells following treatment –induced aplasia or use of growth factors) OR

-Appearance or reappearance of extramedullary disease.

-If there are no circulating blasts and no extramedullary disease and the bone marrow blast percentage is $> 5\%$ but $< 20\%$, then a repeat bone marrow performed at least 7 days after the first marrow examination and documenting bone marrow blast percentage $> 5\%$ is necessary to establish relapse.

E.1.4 Partial Remission (PR):

-Normalization of the peripheral blood absolute neutrophil count $1.0 \times 10^9/L$, platelets $>$ than $100 \times 10^9/L$, and at least a 50% decrease in the percentage of marrow aspirate blasts to 5-25% , or marrow blasts $< 5\%$ with Auer rods.

E.1.5 Cytogenetic Responses

Complete cytogenetic response: An abnormal clone is detected in all metaphases prior to treatment and only normal metaphases are observed in all metaphases following treatment.

Partial cytogenetic response: An abnormal clone is detected in all metaphases prior to treatment

and the post-treatment sample has 50% or fewer abnormal metaphases compared to the pretreatment value.

Cytogenetic non-response: An abnormal clone is detected in all metaphases prior to treatment and neither complete nor partial cytogenetic response is observed in post-treatment specimens Specimens with normal cytogenetic results before treatment will not be evaluated for cytogenetic

response. The method used to determine cytogenetic response will be standard metaphase cytogenetics.

E.1.6 Stable disease:

-Subjects who fail to achieve CR, Cri, or PR and who do not have criteria for PD will be defined as having the stable disease. If the subject dies prior to response assessment at the end of Cycle 1, then they will be classified as “indeterminate”.

E.1.7 Progressive disease (PD): may be defined as ONE of the following:

- $> 50\%$ increase in peripheral blood or bone marrow blasts from best assessment with minimum threshold of 20% blasts in the marrow or $1.0 \times 10^9/L$ blasts in peripheral blood.

-Development of biopsy proven extramedullary leukemia (if the subject has extramedullary

CONFIDENTIAL

This document is confidential. Do not disclose or use except as authorized.

disease at baseline, then PD will be defined by blood and marrow criteria or if new sites of extramedullary disease appear).

-If subject who present with an initial marrow blast percentage sufficiently high to preclude the ability to base disease progression on a >50% increase in marrow blast percentage, disease progression should be based on peripheral blood criteria or development of extramedullary leukemia as above.

E.1.8 Persistent Disease

Hematologic Persistence – Bone marrow or peripheral blasts >5% after d+30 following HCT

CONFIDENTIAL

This document is confidential. Do not disclose or use except as authorized.

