Appendix F: MDS/MPN RESPONSE CRITERIA

(Cheson, *et al.*, 2006)

F.1 Antitumor Effect – Myelodysplastic Syndrome / Myeloproliferative Neoplasm

F.1.1. Complete Remission (CR)

Requires that all of the following be present:

Peripheral Blood Counts:

- Hemoglobin greater than 11 g/dL (untransfused, 4 weeks since last transfusion, subject not on erythropoietin).
- Neutrophils 1,000/mm³ or more (not on a myeloid growth factor)
- Platelets 100,000/mm³ or more (not on a thrombopoietic agent)
- Blasts, 0%
- No dysplasia

Bone Marrow Aspirate and Biopsy:

- Less than 5% myeloblasts
- Normal maturation of all cell lines
- No evidence for dysplasia

When erythroid precursors constitute less than 50% of bone marrow nucleated cells, the percentage of blasts is based on all nucleated cells; when there are 50% or more erythroid cells, the percentage blasts should be based on the nonerythroid cells.

F.1.2 Partial Remission (PR):

Requires that all of the criteria for complete remission be satisfied except blasts decreased by 50% or more over pretreatment. Cellularity and morphology are not relevant. Persisting dysplasia is permitted.

Hematologic Improvement (HI)-major (must have at least one of the three listed below)

must

persist for a minimum of 8 weeks to be considered a confirmed response.

- HI-major Erythroid: For subjects with pretreatment hemoglobin less than 11 g/dL, greater than 2 g/dL increase in hemoglobin; for RBC transfusion-dependent subjects transfusion independence.
- HI-major Platelet: For subjects with a pretreatment platelet count less than 100,000/mm³, an absolute increase of 30,000/mm³ or more; for platelet transfusion dependent subjects, stabilization of platelet counts and platelet transfusion independence.
- HI-major Neutrophil: For absolute neutrophil count (ANC) less than 1000/mm³ before therapy, at least a 100% increase, or an absolute increase of more than 500/mm³, whichever is greater.
- HI-major Trilineage: Trilineage response will require the demonstration of HI-major for each of the blood lineages (erythroid, platelet, neutrophil). Trilineage hematologic improvement will also apply to subjects who achieve adequate counts in all three lineages even if one or more lineages was adequate prior to treatment. Thus, all subjects who normalize all three lineages (within IWG definitions) for 8 weeks, but who do not meet the criteria for PR, will be considered HITrilineage.

F.1.3 Cytogenetic Responses

CONFIDENTIAL

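### AML complete remission (Appendix E, E.1.1 and E.1.2) has no circulating-blast criterion, so a patient with persistent blood blasts can count as CR or CRi at day 43

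*Combined protocol and SAP*

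**What the plan says.** Section 11 sends response classification to Appendix E for AML and to Appendix F for MDS/MPN. Sections 1.3 and 13.3 make the CR/CRi rate at day 43 a secondary endpoint, and Section 13.7 reports it as a proportion with an exact binomial interval.

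The relevant AML definitions in Appendix E are:

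- **E.1.1 (CR):** neutrophils above 1.0 and platelets above 100 (× 10⁹/L), "no residual evidence of extramedullary disease and bone marrow aspirate with" at most 5% blasts, and no Auer rods.
- **E.1.2 (CRi):** waives count recovery and changes nothing else: "Same as CR but without normalization of the peripheral blood absolute neutrophil and platelet" values.
- **E.1.3 (loss of a remission):** met by any one of three findings, namely "Reappearance of leukemic blasts in the peripheral blood", marrow blasts above 5%, or extramedullary disease.
- **E.1.4 (PR):** recovered counts with "at least a 50% decrease in the percentage of marrow aspirate blasts to 5-25" per cent, or marrow blasts below 5% with Auer rods.
- **E.1.8 (hematologic persistence):** "Bone marrow or peripheral blasts >5% after d+30 following HCT".

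For MDS/MPN, Appendix F.1.1 requires 0% blood blasts for CR and, in the marrow, "Less than 5% myeloblasts".

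**The concern.** Relapse, progression and persistence in Appendix E all take account of blasts in the blood. The definition of AML remission does not. A patient whose marrow sample shows at most 5% blasts, but whose blood still carries leukemic blasts, therefore meets the written definition of remission. CRi does not require count recovery either, so low counts do not keep such a patient out of the numerator.

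What is at stake is the meaning of the only response rate the plan reports. Describing preliminary efficacy is a stated purpose of the 10-patient expansion (Sections 5.1.7 and 13.4). The duration of complete response in Section 11 also starts when CR criteria are first met, so a false CR would carry into that measure.

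The picture is possible in this population. Section 3.1.1 admits relapse shown by flow cytometry or by disease-defining mutations, and Section 3.1.7 sets only an upper limit on marrow involvement. Low marrow blast percentages at entry are therefore allowed.

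**Working it through.** The plan gives no assumed or target CR rate, so there is no figure to reproduce. The check applies E.1.1 to E.1.4 and E.1.8 literally to test patients.

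**Does another item close the gap?** The extramedullary item does not. E.1.3 treats the two as separate things: "If there are no circulating blasts and no extramedullary disease and the bone marrow blast percentage is" and so on. No other section adds a blood-blast condition for AML remission.

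**Does the timing in E.1.8 apply?** Section 3.1.2 requires relapse at least 2 months after transplant, so every day-43 assessment falls later than day 30 after transplant.

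**Test patients** (none has Auer rods or extramedullary disease; counts in 10⁹/L):

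| Patient | Neutrophils | Platelets | Marrow blasts | Blood blasts | E.1.1, E.1.2, E.1.4 | E.1.8 |
|---|---|---|---|---|---|---|
| A | 1.5 | 150 | 4% | 3% | CR | not met |
| B | 1.5 | 150 | 4% | 8% | CR | persistence |
| C | 0.4 | 30 | 4% | 8% | CRi | persistence |
| D | 1.5 | 150 | 5% | 0% | CR, and also PR if baseline marrow blasts ≥ 10% | not met |
| E | 0.4 | 30 | 5% | 0% | CRi only (PR needs recovered counts) | not met |

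Patients A to C show the main defect. B and C are responders and in persistence at once.

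Patient D shows the boundary overlap. PR needs a fall of at least half, to 5% or more. Ending at 5% requires a baseline of at least 5% / 0.5 = 10%. With a baseline of 8%, patient D is CR only.

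**Would progression catch patients B or C?** E.1.7 needs a rise of more than 50% from the best assessment, and at least 20% marrow blasts or 1.0 × 10⁹/L blood blasts. At 8% blood blasts, the second threshold is reached only at a white count of 1.0 / 0.08 = 12.5 × 10⁹/L. Stable low-level blood blasts are not progression.

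**Size, with assumed responder counts.** One reclassified patient moves the rate by 1/n:

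- n = 10 (phase 1b): 1/10 = 10 points.
- n = 5 + 10 = 15 (dose level 0 in phase 1a plus phase 1b): 1/15 = 6.7 points.

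The exact 95% limits are the 0.025 quantile of Beta(x, n − x + 1) and the 0.975 quantile of Beta(x + 1, n − x):

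- 5/15 = 33%, interval 12% to 62%
- 4/15 = 27%, interval 8% to 55%
- 3/10 = 30%, interval 6.7% to 65.2%
- 2/10 = 20%, interval 2.5% to 55.6%

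**The case against.** The best defence is that this is a drafting omission and no assessor would call a patient with leukemic blasts in the blood a remission. The word in E.1.3 is reappearance, which presupposes that blasts had cleared. That is a fair reading of intent. But the clearance is nowhere stated as a condition of CR or CRi, and Section 11 classifies patients by the stated definitions. The omission stands.

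Several stronger readings are tempting, and the documents do not support them:

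- **That the same blood film is remission at one visit and relapse at the next.** Blasts that never cleared have not reappeared, so E.1.3 does not say this. The direct conflict is with E.1.8, and only when blood blasts exceed 5%.
- **That the 5% overlap lets leukemia count as remission.** E.1.3 and E.1.8 both start above 5%, so the plan treats exactly 5% as neither relapse nor persistence. The overlap is a boundary ambiguity under narrow conditions. Section 11 takes the best recorded response, which also favours CR, although the day-43 rate is a time-point rate. It matters only because CR enters the numerator and PR does not.
- **That the difference from Appendix F is itself an error.** Section 11 says criteria are disease-specific. The comparison shows only that the pooled rate combines a looser AML standard with a stricter MDS/MPN one.
- **That the trial's response rate is inflated.** The documents give no responder counts, AML share or frequency of this picture. Section 11 also limits who is evaluable for response, so neither 10 nor 15 need be the denominator.

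It is also true that MTD and the phase 2 dose depend on DLTs, and that no threshold is attached to the response rate.

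**Conclusion.** The point holds. As written, E.1.1 and E.1.2 score an AML patient with at most 5% marrow blasts, no Auer rods and no extramedullary disease as CR or CRi whatever the blood shows. When blood blasts exceed 5%, E.1.8 contradicts that result. The CR/PR overlap at exactly 5% is real but minor. It needs recovered counts, no Auer rods, no extramedullary disease and baseline marrow blasts of at least 10%.

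The effect is confined to AML patients and to a secondary, descriptive endpoint, with the duration of complete response following from it. No type I error, power or MTD decision is involved. The shift of 10 or 6.7 points per patient rests on assumed denominators of 10 or 15, and the number of patients affected is unknown. The definition should be corrected because the rate is the plan's only planned measure of response and is estimated from few patients.

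**What to change.** 1. Add to E.1.1 that there are no circulating leukemic blasts. E.1.2 then inherits the condition, and test patients A to C are no longer CR or CRi.
2. In E.1.4, change the PR marrow range to above 5% and up to 25%, and change the Auer-rod clause from below 5% to at most 5%. Both edits are needed. If only the range moved, a patient with exactly 5% marrow blasts and Auer rods would be excluded from CR by the Auer rods and would fit neither PR clause.

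The second change separates CR from PR only. PR and relapse are still told apart by whether CR or CRi came first: a patient who goes from 40% to 3% and then to a confirmed 10% with recovered counts falls in the PR range and also meets relapse.

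The cost is wording in Appendix E. The study calendar (Table 6) already schedules a blood count with differential and a marrow at day 43, so patients already assessed can be reclassified from existing data without new procedures.

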3.1.13 Negative pregnancy test for females of childbearing potential only

3.2 Exclusion Criteria

3.1.14 Extramedullary relapse involving immuno-privileged sites (e.g. CNS, testes, eyes). Other sites of extramedullary relapse (e.g. leukemia cutis, granulocytic sarcoma) are acceptable.

3.1.15 Participants who had cytotoxic chemotherapy or other investigational agents within 4 weeks prior to cell infusion (6 weeks for nitrosoureas or mitomycin C), or immunotherapy within 8 weeks prior, or those who have not recovered from adverse events due to agents administered more than 4 weeks prior. Use of hydroxyurea, HMAS (e.g. azacytidine, decitabine) and/or approved novel agents (e.g. venetoclax, FLT3 inhibitors, IDH1/2 inhibitors etc.) to control counts within 4 weeks prior to cell infusion is permitted.

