5.6 Duration of Therapy

Duration of therapy will depend on individual response, evidence of disease progression, and tolerance. In the absence of treatment delays due to adverse events,

CONFIDENTIAL

This document is confidential. Do not disclose or use except as authorized.

treatment (including induction followed by maintenance therapy) may continue for 60 weeks or until one of the following criteria applies:

- Disease progression (as defined in **Appendices E-F**). As T-cell infiltration of the tumor site (e.g. granulocytic sarcoma, skin) can look like progressive disease, please discuss the results of clinical or radiographic assessments (e.g. leukemia cutis site inflammation; granulocytic sarcoma scans) showing progressive disease with the study PI before removing a patient from the study for disease progression. Patients with radiographic progression who are deriving clinical benefit will be allowed to remain on treatment until the next schedule efficacy assessment.
- Intercurrent illness that prevents further administration of treatment,
- Unacceptable adverse event(s), requiring temporary or permanent stopping of Ipilimumab defined in **Section 6.1.3**
- Participant decides to withdraw from the study, or
- General or specific changes in the participant's condition render the participant unacceptable for further treatment in the opinion of the treating investigator

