Serum Chemistry ⁵	X	X	X	X	X	X	X	X	X	X	X
TSH											X
Chimerism testing		X									X
PB Correlative studies ⁶	X	X ¹²			X ¹²			X			X ¹²
BM aspirate and core ⁷		X			X						X
aGVHD assessment ⁸	X	X	X	X	X	X		X	X	X	X
cGVHD assessment ⁹		X			X			X			X

CONFIDENTIAL

This document is confidential. Do not disclose or use except as authorized.

- * – Patients will be dosed at start of week 1, 4, 7, and 10 (induction) and return for an end of induction response evaluation on start of week 14. Maintenance dosing will then occur at weeks 24, 36, 48 and 60. Patients who experience clinical benefit may continue to receive Ipilimumab q12 weeks till week 60 unless there is unacceptable toxicity, disease progression, or withdrawal of consent.
- **– End of study off-treatment visit will be 3 months after last dose of maintenance Ipilimumab. Note: for IND/IDE trials, follow up visits or other contact are required in order to identify SAEs during the 30 days following the end of study treatment
- 1 – A baseline EKG and cardiac ECHO (or MUGA) is required for all patients, and anytime thereafter as clinically indicated.
- 2 – For those with evidence of CHF, myocardial infarction, myocarditis or cardiomyopathy at any time during the study, a detailed cardiac evaluation including labs (CPK, Troponin), cardiology consult, with EKG and ECHO (or MUGA) at minimum is required, as clinically indicated. Please refer to **Section 6.1.13** for guidance on cardiac toxicity management for Ipilimumab.
- 3 – For females of childbearing potential only
- 4 – O_2 Saturation on room air required only at screening; Weight on day closest prior to infusion will be used for study dosing calculations, height only needs to be collected at screening.
- 5 – Includes: comprehensive metabolic panel, LFTs, magnesium, phosphorus, uric acid, LDH, lipase, eGFR
- 6 – See **Section 9.1.1**.
- 7 – See **Section 9.1.2 and 9.1.3**. If there is no bone marrow involvement at baseline and/or extra-medullary disease is documented, the other sites of disease relapse will be assessed as clinically appropriate (**section 9.1.3** e.g. measurement of lesions of leukemia cutis including skin biopsy, PET/CT assessments for other extramedullary sites (e.g. granulocytic sarcoma)
- 8 – See **Appendix C** for aGVHD assessment
- 9 – Per NIH consensus criteria for cGVHD assessment
- 10 – Viral Panel includes HIV, Hep B and C
- 11 – Exception under 9.1.1 a). Draw a PASQ6P
- 12 – Exception under 9.1.1 b). Draw a PASQ4P

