11. MEASUREMENT OF EFFECT / CLINICAL RESPONSE

Evaluable for toxicity- Participants who receive cell infusion at the specified dose plus Ipilimumab will be evaluated for toxicity. Evaluable patients are those who experience a DLT before day 43, or are assessable for DLT at day 43. Phase 1a patients who are unevaluable for DLT may be replaced.

Evaluable for response- Only those participants who have measurable disease present at baseline, have received cell infusion at the specified dose and least two cycles of Ipilimumab therapy, and have had their disease re-evaluated will be considered evaluable for response. These participants will have their response classified according to the disease-specific definitions stated in **Appendices E-F**. Patients unevaluable for response will not be replaced.

Response Criteria will be disease-specific, and are provided in detail in the following appendices:

- **Appendix E:** Acute Myelogenous Leukemia
- **Appendix F:** Myelodysplastic Syndrome / Myeloproliferative Neoplasm

Evaluation of Best Overall Response The best overall response is the best response recorded from the start of the treatment until disease progression/recurrence (taking as reference for progressive disease the smallest measurements recorded since the treatment started). The participant's best response assignment will depend on the achievement of both measurement and confirmation criteria

Duration of overall response: The duration of overall response is measured from the time measurement criteria are met for CR or PR (whichever is first recorded) until the first date that recurrence or PD is objectively documented, taking as reference for PD the smallest measurements recorded since the treatment started.

Duration of overall complete response: The duration of overall CR is measured from the time measurement criteria are first met for CR until the first date that recurrent disease is objectively documented.

Progression-Free Survival (PFS) is defined as the duration of time from start of treatment to time of objective disease progression or death whichever occurs first.

Overall Survival (OS) is defined as the duration of time from start of treatment to time of death.

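### In AML with extramedullary disease at baseline, growth of the existing lesion is not a progression criterion, so some patients whose disease is growing are scored stable and progression-free

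*Combined protocol and SAP*

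**What the plan says.** **Eligibility.** Section 3.1.1 accepts relapse shown in marrow or at extramedullary (EM) sites. The exclusion list (3.1.14) rules out immune-privileged sites and then says "Other sites of extramedullary relapse (e.g. leukemia cutis, granulocytic sarcoma) are acceptable".

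**Assessment.** Footnote 7 of the study calendar (Section 10) foresees patients with no marrow involvement. For them, or where EM disease is documented, it says "the other sites of disease relapse will be assessed as clinically appropriate", with skin-lesion measurement, skin biopsy and PET/CT as examples.

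**Progression in AML.** The general limb of E.1.7 requires a rise of more than 50%, worded as "increase in peripheral blood or bone marrow blasts from best assessment with minimum threshold of 20% blasts in the marrow", or 1.0 x 10^9/L blasts in blood. For a patient with EM disease at baseline, the next limb says "disease at baseline, then PD will be defined by blood and marrow criteria or if new sites of extramedullary disease appear".

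**Default category.** E.1.6 says "Subjects who fail to achieve CR, Cri, or PR and who do not have criteria for PD will be defined as having the stable disease".

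**Use of these definitions.** Section 11 classifies response by Appendices E-F. It defines PFS as time to objective progression or death and gives no separate definition of progression. Section 5.6 also takes progression from Appendices E-F. It then asks for clinical or radiographic findings at sites such as leukemia cutis or granulocytic sarcoma to be discussed with the study PI, and adds "Patients with radiographic progression who are deriving clinical benefit will be allowed to remain on treatment until the next schedule efficacy assessment".

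**The concern.** The plan admits patients whose only disease may be a skin lesion or a sarcoma and provides for measuring it, but gives that measurement no role in scoring progression. Read literally, E.1.7 makes growth at the only disease site a non-event.

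The endpoints at stake are PFS at day 92 and at week 60, both secondary. The error has one direction: it can only make PFS look better. There is also a reproducibility problem. An assessor who relies on E.1.7 and one who relies on the language of 5.6 could reach different progression dates from the same scan.

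**Working it through.** The plan states no figure on this point, so there is nothing to reproduce. The check sets the rules side by side and then gives a sense of scale.

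**1. Following one patient through the rules.** Take an AML patient with leukemia cutis, a clear marrow and no blood blasts, whose skin lesion enlarges steadily.

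- *E.1.7, blood and marrow limb:* not met. Blasts reach neither 20% in marrow nor 1.0 x 10^9/L in blood.
- *E.1.7, EM limb:* not met. No new site has appeared.
- *E.1.3, relapse:* does not apply. EM appearance or reappearance counts only after CR or CRi, which this patient never reached.
- *E.1.1, E.1.2 and E.1.4, remission:* not met. CR and CRi need no residual EM disease, and PR is defined by "at least a 50% decrease in the percentage of marrow aspirate blasts".
- *E.1.6:* the patient is stable disease by default and has no PFS event.

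The same holds for a patient with both marrow and EM disease if only the existing lesion progresses and no remission category is met.

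**2. The other passages.** Section 5.6 warns that T-cell infiltration of a tumor site may mimic progression and gives inflammation at a leukemia cutis site as an example. That warning has a purpose only if a change at an existing site could otherwise be called progression, which E.1.7 does not allow. Section 11, when defining best response, describes the reference as "taking as reference for progressive disease the smallest measurements recorded since the treatment started". This fits lesion measurement, but the section sets no lesion criterion. Appendix F (F.1.4) lists blasts, granulocytes or platelets, and hemoglobin or transfusion dependence, with no EM criterion of any kind.

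**3. Chance that at least one EM-only patient is enrolled.** The EM-only share p is not in the documents, so 5%, 10% and 20% are assumed. The cohort is n=10 (phase 1b, Section 5.1.7), or n=15 when the 5 evaluable patients at dose level 0 (amendments in Section 13.4) are added. The formula is 1 - (1 - p)^n.

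| Assumed p | n=10 | n=15 |
|---|---|---|
| 5% | 1 - 0.95^10 = 40% | 1 - 0.95^15 = 54% |
| 10% | 1 - 0.90^10 = 65% | 1 - 0.90^15 = 79% |
| 20% | 1 - 0.80^10 = 89% | 1 - 0.80^15 = 96% |

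This is the chance of enrolling such a patient, not of misclassifying one. Misclassification also requires the lesion to grow with no other event.

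**4. Effect of one misclassified patient.** With no censoring before the landmark, the shift is 1/n: 1/10 = 10 points, 1/15 = 6.7 points. For illustration, assume 40% are scored progression-free (exact 95% intervals):

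- n=10: 4/10 = 40% (12-74%) becomes 3/10 = 30% (7-65%).
- n=15: 6/15 = 40% (16-68%) becomes 5/15 = 33% (12-62%).

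**The case against.** **The restriction may be deliberate.** Section 5.6 warns of inflammatory change, and Section 2.2.2 reports a tumor flare in a breast lesion followed by a 27% decrease. This is a good reason to require confirmation before scoring progression. It does not justify excluding lesion growth for good, even when it persists or is proven by biopsy.

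**The passages may be compatible.** A scan can show progression through a new site, which E.1.7 counts, and the Section 11 reference resembles the best-assessment wording of E.1.7. PFS also refers to objective progression without naming Appendix E, so an assessor might score lesion growth anyway. This softens the conflict but does not remove it: Appendices E-F are the only progression criteria given, and the example in 5.6 concerns an existing site.

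**The gap is narrow.** This stands. Patients who reach CR or CRi are covered by E.1.3, and any patient can still progress through blood, marrow or new sites.

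**The effect is small beside the uncertainty.** This also stands in part. The analysis is descriptive, and the intervals above are far wider than a one-patient shift. The bias nevertheless has a known direction and can be avoided.

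**Stronger readings that a reader might infer, and that the documents do not support:**

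- *Different study sites would score differently.* The trial is single-center, and 5.6 sends doubtful cases to the study PI. The risk is inconsistency between assessors or occasions.
- *Responder groups for the correlative work would change.* Moving a patient from stable to progressive disease leaves that patient a non-responder in any grouping based on CR or PR. PR is marrow-based, but it is not a named secondary endpoint.
- *The sponsor's earlier ipilimumab study gives the affected share.* Its 4 of 12 AML patients (3 leukemia cutis, 1 myeloid sarcoma) had EM disease of some kind. The EM-only share is not given, and this trial also enrols MDS and MPN.

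**Conclusion.** The point holds as a defect in a stated rule. For AML patients with baseline EM disease who do not reach CR or CRi, E.1.7 and E.1.6 together score growth confined to an existing lesion as stable and progression-free. This conflicts with 5.6 and sits poorly with Section 11. Appendix F leaves the same gap for MDS and MPN.

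The wording gap is certain; its numerical effect is not. The enrolment probabilities of 40-89% (n=10) and 54-96% (n=15) rest on an assumed EM-only share of 5-20%. The shift of about 10 or 6.7 points per patient assumes no censoring, and no death or other progression event before the landmark.

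The effect is limited to PFS at day 92 and week 60. The MTD is set by DLTs, which this rule does not define. The day-43 CR/CRi rate is safe because both categories already require that no EM disease remains. The stable-disease label also bears on stopping treatment (5.6) and on entry to maintenance (Section 10). Those are clinical decisions, and no view is taken on them here.

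**What to change.** For scoring the day 92 and week 60 PFS endpoints, amend E.1.7, and add a matching criterion to Appendix F, along these lines:

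- Unequivocal growth of a baseline EM lesion over its smallest recorded measurement is a progression event.
- It must be confirmed at the next scheduled assessment, or by biopsy where one is done, to exclude T-cell infiltration.
- The event is dated at the first measurement that showed the growth.
- The sponsor sets the growth threshold in advance. The documents give no basis for a particular figure for lesion size.

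Reconcile E.1.7 with Sections 5.6 and 11 so that all three describe the same progression event. How progression affects continued treatment or maintenance is for the sponsor to reconcile; no clinical rule is proposed.

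The cost is mainly appendix wording. There may be a few more PFS events, and some calls will wait for confirmation. Footnote 7 leaves lesion assessment to clinical judgement, and Section 9.1.3 makes biopsy depend on safety and feasibility, so some patients may lack a full series of measurements.
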